#### 6.4. STUDY DESIGN

This single-subject case series will utilize an ABA design, where the intervention phase (b) is sandwiched between an initial baseline period (a) and post-intervention/return-to-baseline period (a). Each baseline period will last for one-week and involve unrestricted standard care. The intervention period will last for three-weeks, allowing a one-week acclimatization period before a two-week full-scale wearing protocol (if tolerable to the child). The full-scale wearing protocol was defined – through analysis of existing testimonial data, and consultation with JettProof and prescribing clinicians – as a minimum 6 hours/day of continuous wear. The participants will comprise children aged 4 years 0 months to 11 years 11 months with an existing community diagnosis of autism spectrum disorder (see Section 6.8. for a full description of trial inclusion/exclusion criteria). Child participants will attend six face-to-face assessment sessions with their caregiver(s): upon study entry (week 0), during pre-intervention/baseline phase A (week 1), pre-intervention/acclimatization phase B (week 2), intervention phase A (weeks 3 and 4), and post-intervention/return to baseline phase A (week 5).

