#### *6.6.E. STRATEGIES TO IMPROVE/MONITOR ADHERENCE*

After the researcher has supplied child participants their singlet and supported their first wear, they will provide the caregiver with strategies to support and encourage their child's singlet wearing and manage challenging behaviour should it arise. A researcher will telephone the caregiver at least three times during the intervention phase – once each during each of the acclimatization and full-scale wearing weeks – to check how the child is doing and troubleshoot any issues arising. During the intervention phase, the length of time the child spends wearing the singlet will be reported each day by the caregiver via a smartphone-based experience sampling app.

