#### *6.8.B. INTERVENTION SCHEDULE*

The end of the week 0 visit will mark the beginning of the trial period, and first intervention phase. Children will continue with their standard care for the first trial week (i.e., week 1; pre-intervention/baseline phase A), with no restrictions on concomitant care or intervention (including medications). Week 2 will be a period of acclimatization (pre-intervention/acclimatization phase B), allowing children to practice wearing the singlet and increase the duration of daily use in their own time. The researcher will telephone the caregiver during this week to check how they are doing and to troubleshoot any issues, completing a further follow-up call if needed. Weeks 3 and 4 will be the full intervention phase (intervention phase B), whereby children are encouraged to wear their singlet for as long as they feel comfortable. There will be no restrictions regarding wearing times or contexts, nor regarding access to outside care or interventions, during the intervention phases. Children will cease wearing their singlet and return to their standard care in week 5.

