#### *6.8.C. ASSESSMENT SCHEDULE*

Child participants will attend six face-to-face assessment visits (See Figure 1 & Table 1) with their caregiver(s) during each of the trial weeks. Assessment visits at weeks 1 through 5 will each involve a researcher fitting the child with an Empatica E4 wristband on the wrist or calf. Empatica E4 recordings will be taken while children watch a low-demand movie (Inscapes) to ascertain their physiological baseline, and while completing Lab-TAB (H. Goldsmith et al., 2010) episodes interspersed with a period

of free-play with their caregiver. Additional assessments conducted at weeks 1 and 5 include the M-ABC-2 and COMPS-2, and at week 5 an examiner-led interview to explore child and caregiver perceptions and experiences of the singlet. All assessment sessions will be video-recorded with consent from caregivers for later scoring.

The caregiver will be given a laptop during each of their child's assessment visits and navigated to a REDCap survey to complete: GAS (Kiresuk & Lund, 1994) in weeks 1 through 5, in addition to the SCAS-P (Nauta et al., 2004), PES (Pfeiffer et al., 2017). Additionally, the PSI-4-SF (Abiden, 2012) will be completed via hardcopy in weeks 1 and 5. Caregivers who do not manage to complete all survey measures during their child's assessment visit will be provided a survey return code, enabling them to return to the survey for later completion (within 24 hours). The PSI-4-SF may be taken home for completion and return at the child's next assessment visit. Assessment visits in Weeks 2, 3 and 4 will require a time commitment of around one hour for children and their caregiver(s). A longer time commitment of two hours will be required for visits in Weeks 1 and 5.

During the trial period, the caregiver will receive a push notification on their smartphone from their installed MyCap application three times per day (morning, afternoon, evening) to report their child's previous night's sleep (morning, only), current activity, affect, use of non-routine medications (evening, only), and singlet wearing (intervention phases, only). The resulting daily time commitment for caregivers will be approximately 6 minutes (2 minutes per day).

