### 7.1.B. PLANS TO PROMOTE PARTICIPANT RETENTION AND COMPLETE FOLLOW-UP

Participants who deviate from the protocol will not be withdrawn from the trial. Upon trial completion, each participant will retain their singlets and be provided a \$200 (AUD) gift voucher -- \$100 AUD to the child and \$100 AUD to the caregiver – to thank them for their time.

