### 7.5. ADVERSE EVENTS AND SAFETY

The deep-touch compressive pressure produced by the singlet might cause minor physical discomfort and/or secondary physical sensations (e.g., itching, tingling) arising from the activation of sensory nerve endings in the skin. Qualitative work we have performed in preparation for this study – i.e., focus group discussions with clinicians who prescribe JettProof garments, thematic analysis of customer testimonials posted to the JettProof website – suggests that discomfort is experienced for a small proportion of wearers and is likely to resolve over time as acclimatization occurs. For this reason, children's first wear of the singlet will be supervised by a trained occupational therapist and a one-week acclimatization period will allow gradual increased exposure to the singlet before proceeding to full-scale wearing (i.e.,  $\geq 6$  hours per day). A researcher will telephone each caregiver at least once per week during the intervention phase (i.e., three times in total) to monitor for the occurrence of any adverse events associated with the singlet.

Our qualitative work has indicated that caregiver attempts to doff JettProof garments (e.g., for laundering) may be met with child refusal, upset (e.g., crying) and other challenging behaviour (e.g., tantrum). As such, each family will be provided three singlets for the intervention phase, allowing

substitution while laundering. Further – in an effort to make trial events more predictable for child participants and ensure ample time for them to prepare for transitions across trial phases – each child will be given a printed visual schedule at the beginning of the trial to take home with them, that illustrates the sequence of study activities and singlet wearing. This schedule will be reviewed at each study visit with the child and with the caregiver by phone as needed by the trained occupational therapist research assistant. Lastly, a researcher will telephone each caregiver during their child’s post-intervention/return to baseline phase to monitor for the occurrence of adverse events associated with *removal* of the singlet.

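### The daily singlet-wear item stops before week 5, so adherence to the withdrawal phase of the ABA design is not systematically recorded

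*Protocol*

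**What the plan says.** Protocol 6.4 sets an ABA design with no control group. Of the A phases it says "Each baseline period will last for one-week and involve unrestricted standard care". Of the B phase it says "The intervention period will last for three-weeks, allowing a one-week acclimatization period before a two-week full-scale wearing protocol".

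For the second A phase, 6.8.B states: "Children will cease wearing their singlet and return to their standard care in week 5".

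Duration of wear is captured through the caregiver's smartphone app. Section 6.6.E says "During the intervention phase, the length of time the child spends wearing the singlet will be reported each day by the caregiver". Section 6.8.C has the app prompt "three times per day (morning, afternoon, evening" during the trial period, but limits one item: "singlet wearing (intervention phases, only". Table 1 (7.1.A) shows the app running daily in weeks 1 to 5.

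On removal, 7.5 reports from preparatory qualitative work that "caregiver attempts to doff JettProof garments (e.g., for laundering) may be met with child refusal". It gives each family three singlets for the intervention phase so that one can be swapped in during washing. It also plans a visual schedule and a week 5 call about adverse events of removal. Section 7.1.B keeps participants who deviate from the protocol in the trial and says that, once the trial is complete, "each participant will retain their singlets". Section 6.6.D has compliance monitored at each weekly visit or by telephone.

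**The concern.** Each child is their own control (6.2), so the return to baseline is what helps to separate a singlet effect from time, practice and habituation to the tasks. The testimonial analysis in 6.1 points to an effect present only while the garment is on, so a reversal in week 5 is the pattern to look for. A missing reversal can be interpreted only if the child is known to have been off the garment.

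The same week also supplies the second reading of every measure taken only in weeks 1 and 5: M-ABC-2 and COMPS-2 (a primary outcome), SCAS-P, PES and PSI-4-SF. If week 5 wear is unknown, the analyst cannot tell whether a change on these is an on-garment effect, a lasting effect, or neither. Continued wear can mislead in two directions: it hides a reversal in the weekly series, and it can look like lasting benefit in the week 1 to week 5 comparison.

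**Working it through.** **1. The plan's own figure.** The Synopsis gives 2 minutes per app input and 3.5 hours in total. With 5 weeks, 7 days and 3 prompts a day: 5 × 7 × 3 = 105 prompts, and 105 × 2 / 60 = 3.5 hours. The figure reproduces only if all 35 days are counted, so the week 5 prompts are already budgeted.

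**2. Coverage of the wear item.** The intervention phases are weeks 2 to 4.
- Now: 3 × 7 = 21 of 35 days, and 0 of the 7 withdrawal days.
- With week 5 added: 4 × 7 = 28 of 35 days, and 7 of the 7 withdrawal days.
- The remaining 7 days are week 1, before the singlet is introduced. Earlier users of sensory garments are excluded (6.6.B), so wear in that week is not a practical concern.

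**3. Other week 5 contacts that might capture wear.**
- Compliance monitoring (6.6.D): covers compliance in general; no quantity is specified.
- Week 5 visit (6.8.C): video-recorded, but the singlet may be worn under other clothing (6.6.C), and no check of whether it is on is described.
- Week 5 interview (6.8.C): perceptions and experiences.
- Week 5 call (7.5): adverse events of removal.

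Any of these may bring continued wear to light. None is said to yield days or hours, which is what classifying seven days of affect and sleep reports requires.

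**4. Illustration of the effect for one child.** The documents give neither an effect size nor a rate of continued wear, so both are assumed. Let d be the true on/off difference and f the share of usual wear that continues in week 5. Assume that effect is proportional to wear, with no carry-over and no time trend. Then:
- apparent reversal (B minus second A) = d × (1 − f)
- apparent week 1 to week 5 change = d × f

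| f | Reversal, d = 0.8 | Week 1 to 5 change, d = 0.8 | Reversal, d = 0.5 | Week 1 to 5 change, d = 0.5 |
|---|---|---|---|---|
| 0% | 0.80 | 0 | 0.50 | 0 |
| 25% | 0.60 | 0.20 | 0.375 | 0.125 |
| 50% | 0.40 | 0.40 | 0.25 | 0.25 |
| 75% | 0.20 | 0.60 | 0.125 | 0.375 |
| 100% | 0 | 0.80 | 0 | 0.50 |

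The table shows direction and mechanism. Without week 5 wear data, nobody could say which row applies to a given child.

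**The case against.** The best defence is that continued wear would probably be noticed. Compliance is monitored weekly, and week 5 has a face-to-face visit, an interview about the singlet and a call devoted to its removal. That stands against any claim that continued wear would go unseen. It does not answer the narrower point that the amount is not recorded.

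Three stronger readings are tempting, and the documents do not support them.
- A reader might infer that the protocol expects refusal in week 5. Section 7.5 says only that refusal may occur, gives laundering as its example, and sets out mitigation. The three singlets are there for washing.
- A reader might infer that the garments are stated to be at home in week 5. Section 7.1.B says families keep them once the trial is complete. That they are at home during week 5 is an inference from the absence of any collection step: reasonable, but not stated.
- A reader might put a group figure on the loss, for example 30% of the B to second A contrast if 3 of 10 children keep wearing the singlet fully (1 − 3/10 = 0.70 retained). That restates an assumed rate and assumes equal effects, whereas 7.3.A examines each participant's own series. Nor do the documents show that the children most attached to the garment respond best.

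It is also fair to say that this is a feasibility study of 10 children seeking preliminary estimates (6.9), and that sensitivity analyses commonly belong in a statistical analysis plan. The first limits the consequence. The second does not apply to the core point, because restricting the wear item is a data-capture rule that the protocol itself fixes, and days not recorded cannot be reliably recovered later.

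**Conclusion.** The point holds in a limited form. The protocol assigns non-wear in week 5 and explicitly switches off the only planned daily measure of wear for that week, leaving 0 of 7 withdrawal days covered. Continued wear is plausible on the protocol's own account, though neither predicted nor quantified there. If it occurs, it shrinks that child's reversal and blurs the meaning of the week 1 to week 5 measures, by an amount that the planned data could not establish. How far depends on how much wear continues and on whether effect follows wear. Every percentage here is illustrative. The change is worth making because it is cheap and bears on the comparison that gives the ABA design its inferential value.

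**What to change.** - In 6.8.C, replace the restriction of the wear item to the intervention phases with weeks 2 to 5, and align 6.6.E. This changes what is recorded and leaves the wearing rule as it is.
- Record at the week 5 visit whether the singlet is on.
- Report week 5 wear for each child beside that child's A-B-A series.
- If the contrast is repeated using only children with no reported week 5 wear, label it a sensitivity analysis. State that it selects on a post-treatment variable that may be related to response.

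Cost: one existing item for seven more days, within prompts already scheduled. The totals stay at 105 prompts and 3.5 hours at the stated 2 minutes per input. The visit check and the per-child report each add a line.

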## 6.9. SAMPLE SIZE

In this feasibility study, we will recruit 10 participants in order to provide initial insights into the intervention feasibility and protocol as well as preliminary effect size estimates in the context of pragmatic constraints (i.e., time, budget).

## 6.10. RECRUITMENT

Recruitment into the study will be through existing participant registries at LTU, and announcements posted on social media, private therapy practices and University noticeboards. The final sample will be purposively selected to include children with a range of sensory processing challenges – as ascertained by the SSP (McIntosh et al., 1999) completed by caregivers at eligibility screening – to allow exploration of differential responsiveness.

# 7. METHODS: DATA COLLECTION, MANAGEMENT, ANALYSIS

## 7.1. DATA COLLECTION METHODS

### 7.1.A. PLANS FOR ASSESSMENT AND COLLECTION OF STUDY DATA

Study data will be collected through online survey platforms (REDCap, Pearson's Q-global) in lieu of/in addition to paper forms, smartphone-based experience sampling, and face-to-face assessments. The assessment schedule is outlined in Tables 1 and 2.

**Table 1.** Schedule of Assessments.

Trial Week	0	1	2	3	4	5
Caregiver-report measures						
Inclusion/ exclusion criteria	X					
SRS-2	X					
SSP	X					
PPECS	X					
Demographic and medical history questionnaire	X					
Interview	X					X
Vineland-3	X					
SCAS-P		X				X
PES		X				X
PSI-4-SF		X				X
GAS		X	X	X	X	X
ESM		X (Daily)	X (Daily)	X (Daily)	X (Daily)	X (Daily)
Child Assessment Measures						
M-ABC-2		X				X
COMPS-2		X				X
Interview	X					X
Physiological recording		X	X	X	X	X
Lab-TAB		X	X	X	X	X

**Table 2.** Summary of Measures.

Caregiver-Report Measures			
Measure	Description	Variable	Role
Demographic and Medical History Questionnaire	Caregiver-report on child and family background information and child medical history	Various demographic characteristics for child and family	Sample characterisation
Social Responsiveness Scale-2 nd Edition (SRS-2; Constantino & Gruber, 2012)	Caregiver-report measure of child autism features	Total raw and t score	Eligibility; Sample characterisation
Short Sensory Profile (SSP; McIntosh et al., 1999)	Caregiver-report measure of child sensory processing	Domain raw scores; Domain standard scores; Sensory subtype (Lane et al., 2014);	Eligibility; Sample characterisation

		Overall score	
Pragmatics Profile of Everyday Communication (PPECS; Dewart & Summers, 1995)	Examiner-led interview to gain a qualitative picture of children's typical communicative behaviours.	Qualitative responses to interview questions	Eligibility; Sample characterisation
Vineland Adaptive Behaviour Scales-3 rd Edition (Vineland-3; Sparrow et al., 2016)	Caregiver-report measure of child adaptive behaviour	Domain Age-Equivalence and Standard Scores (SS); Total SS	Sample characterisation
Spence Children's Anxiety Scale-Parent Version (SCAS-P; Nauta et al., 2004)	Caregiver-report measure of child anxiety symptoms	Total raw and t score; Subscale raw and t scores	Outcome
Parent Effort Scale (PES; Pfeiffer et al., 2017)	Caregiver-report measure of effort expended to support child participation in home and community activities	Subscale raw and standard scores; Overall raw and standard score	Outcome
Parent Stress Index-4 th Edition Short Form (PSI-4-SF; Abiden, 2012)	Caregiver-report measure of caregiving stress	Domain standard scores; Overall standard score	Outcome
Goal Attainment Scaling (GAS; Kiresuk & Lund, 1994)	Caregiver-report measure of child goal attainment	Change scores	Outcome
Interview	Examiner-led interview to ascertain caregiver's motivations and experiences	Qualitative responses to interview questions	Feasibility/acceptability

**Child Assessment Measures**

Assessment Tool	Description		
Movement Assessment Battery for Children-2 nd Edition (M-ABC-2; Henderson et al., 2007)	Standardized direct assessment of child motor function	Component standard scores; Total standard score	Outcome
Clinical Observations of Motor and Postural Skills-2 nd Edition (COMPS-2; B Wilson et al., 2000)	Observational direct assessment of child motor and postural skills	Domain score; Total score	Outcome

**Study Name:** Effectiveness of JettProof Sensory Singlets for Autistic Children: A Single Case Series

**Protocol Number:** N/A

**Version & date:** version 2, dated 18th July 2022

Empatica E4	Wearable biosensor to collect peripheral physiological arousal and motion activity	Heart rate; Heart rate variability; Electrodermal activity; Motion-based activity	Outcome
Laboratory Temperament Assessment Battery (Lab-TAB; H. Goldsmith et al., 2010)	Standardized direct assessment of child self-regulation	Task scores; Composite score	Outcome
Interview	Examiner-led interview to ascertain children’s own motivations and experiences	Qualitative responses to interview questions	Feasibility/acceptability

### 7.1.B. PLANS TO PROMOTE PARTICIPANT RETENTION AND COMPLETE FOLLOW-UP

Participants who deviate from the protocol will not be withdrawn from the trial. Upon trial completion, each participant will retain their singlets and be provided a \$200 (AUD) gift voucher -- \$100 AUD to the child and \$100 AUD to the caregiver – to thank them for their time.

## 7.2. DATA MANAGEMENT

All study data will be coded with a participant ID number in a location separate to identifiable personal information (e.g., consent forms, contact details). All participant information and data will be entered directly into REDCap (Research Electronic Data Capture – Vanderbilt University, hosted at LTU) by the investigators or caregivers through self-administered online survey. To ensure data quality, the database will be designed with branching logic, data validation, and range checks for data values, where possible. All hardcopy data will be stored in a locked filing cabinet at LTU. Access to data will be limited to research investigators as approved by the HREC. All data will be re-identifiable.

## 7.3. STATISTICAL METHODS

### 7.3.A. OUTCOME ANALYSES

This single-case feasibility study will combine visual and quantitative analyses of the data. For each participant, scores for each repeated outcome measure (i.e., Empatica E4 recordings, Lab-Tab, GAS, PES-H, PES-C, PSI-4-SF) will be graphically depicted as a time-series with standard deviation bands around each series and the global average for each outcome measure plotted as a reference line. Visual analysis will be employed for an initial examination of within-subject slope and level change across trial phases. Effect sizes will be computed through parametric methods (i.e., standard mean difference [Hedges *g*]) and non-overlap indices (e.g., Tau-U), with a *p*-value of < .05 indicative of statistical significance.

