## 6.7. OUTCOMES

### 6.7.A. PRIMARY OUTCOMES

The primary outcomes for this trial are:

- Child sympathetic nervous system activity (i.e., heart rate, heart rate variability, electrodermal activity, and motion-based activity) acquired from an Empatica E4 wristband, worn in the context of Laboratory Temperament Assessment Battery (Lab-TAB; H. Goldsmith et al., 2010) episodes conducted in weeks 1 through 5. Empatica E4 recordings have been shown to accurately predict affective behaviour in autistic children (Goodwin, Mazefsky, Ioannidis, Erdogmus, & Siegel, 2019) and has been validated against other stationary and wearable biosensors (Schuurmans et al., 2020; van Lier et al., 2020).
- Child motor coordination as measured by the standardized Movement Assessment Battery for Children-2nd Edition (M-ABC-2; Henderson, Sugden, & Barnett, 2007) and Clinical Observations of Motor and Postural Skills (COMPS-2; B Wilson, Kaplan, Pollock, & Law, 2000) in weeks 1 and 5. The M-ABC-2 is one of the most widely used motor assessments in research and clinical practice (Barnett, 2008) with evidence of inter-rater reliability, test-retest reliability, content- and concurrent validity (Henderson et al., 2007). The COMPS-2 was designed to supplement standardized measures of motor performance and has demonstrated good inter-rater reliability, test-retest reliability, and construct validity (Brenda Wilson, Pollock, Kaplan, Law, & Faris, 1992).
- Child attainment of individualized and meaningful intervention goals as measured by Goal Attainment Scaling (GAS; Kiresuk & Lund, 1994). Upon study entry, the caregiver of each child will be supported by investigators to formulate two GAS goals centred around self-regulation difficulties for their child and develop a five-point descriptive rating scale for completion in weeks 1 and 5. Use of GAS is common in research and clinical practice and is especially sensitive to capturing change in intervention studies (McLaren & Rodger, 2003).

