### 6.7.B. SECONDARY OUTCOMES

The secondary outcomes for this trial are:

- Child anxiety as measured by the caregiver-reported Spence Children's Anxiety Scale-Parent Version (SCAS-P; Nauta et al., 2004) in weeks 1 and 5. The SCAS-P has strong properties (Nauta et al., 2004; Orgiles, Fernandez-Martinez, Guillen-Riquelme, Espada, & Essau, 2016) including good internal consistency and convergent, divergent and discriminant validity among autistic children (Magiati et al., 2017).
- Child affect and sleep reported daily by caregivers via smartphone-based experience sampling. The experience sampling method demonstrates high ecological validity, in that it captures real-life experiences and behaviours across a full range of momentary contexts while 'in-the-moment', thus circumventing potential biases from retrospective recall.
- Child reactivity and self-regulation as coded from behaviour during semi-structured Lab-TAB (H. Goldsmith et al., 2010) episodes in weeks 1 through 5. Being a direct observational method, the Lab-Tab will provide a method by which to build upon and complement caregiver

ratings of child affect. Lab-TAB episodes have been validated as effective for inducing emotional reactivity in autistic children (Macari, Verneti, & Chawarska, 2021; Northrup et al., 2020) and used previously as a context for physiological recording (Nuske et al., 2022).

[figure not shown]

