### 7.3.B. ADDITIONAL ANALYSES

The sample will be characterized using descriptive methods (Demographic and Medical History Questionnaire, PPECS) and standard/raw scores (SSP, Vineland-3, M-ABC-2). Feasibility and acceptability of the intervention will be determined by participants' daily duration of singlet wear and qualitative responses to the semi-structured interview conducted post-intervention.

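### The list of repeated outcome measures in section 7.3.A does not match the protocol's own outcomes and schedule: it leaves out the primary motor measures, anxiety, daily affect and sleep, and includes caregiver scales measured only twice

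*Protocol*

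**What the plan says.** Section 7.3.A plans, for each child, that "each repeated outcome measure (i.e., Empatica E4 recordings, Lab-Tab, GAS, PES-H, PES-C, PSI-4-SF) will be graphically depicted as a time-series", with SD bands and visual analysis of slope and level across phases. A following sentence plans effect sizes (Hedges g and non-overlap indices such as Tau-U, with p below .05 as the criterion) and names no measures.

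Section 6.7.A makes motor function a primary outcome: "Child motor coordination as measured by the standardized Movement Assessment Battery for Children-2", together with COMPS-2, both taken "in weeks 1 and 5. The M-ABC-2 is one of the most widely used motor assessments". Section 6.7.B lists anxiety on SCAS-P, taken "in weeks 1 and 5. The SCAS-P has strong properties", and "Child affect and sleep reported daily by caregivers via smartphone-based experience sampling". Section 6.7.C places caregiver effort (PES) and caregiver stress (PSI-4-SF) among the other outcomes, at weeks 1 and 5. Section 6.8.C says of PSI-4-SF that it "will be completed via hardcopy in weeks 1 and 5". Table 1 gives the same two weeks for all five instruments.

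Within section 7.3, M-ABC-2 is named once, in 7.3.B, where the sample is described through "standard/raw scores (SSP, Vineland-3, M-ABC-2" and other descriptive data. Experience sampling is named once, in the missing-data rule of 7.3.C. COMPS-2 and SCAS-P are not named at all.

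**The concern.** The list follows no consistent rule. If two observations make a measure repeated, then M-ABC-2, COMPS-2 and SCAS-P belong in it, because they share the schedule of PES and PSI-4-SF. If two observations are not enough, PES and PSI-4-SF do not belong. The daily diary is repeated on any definition and is absent. Outcomes that section 6.7.C ranks lowest are listed, while a primary outcome is not.

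The motor half of the primary objective in section 6.3, and the hypotheses on anxiety, affect and sleep, are at stake: no stated analysis is attached to them. The plan also sets a last-observation-carried-forward rule for diary ratings that it nowhere says it will analyse. Meanwhile the single-case methods are assigned to series that cannot carry them. An analyst would have to depart from the text for PES and PSI-4-SF, and would be free to choose a method for a primary outcome after seeing the data.

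**Working it through.** There is no power or sample-size figure to reproduce; section 6.9 justifies 10 children on feasibility grounds. The check is a count of observations per child and phase, followed by what each planned statistic needs.

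**Inputs.** Phases are from sections 6.4 and 6.8.B: A1 = week 1, B = weeks 2 to 4, A2 = week 5. Visits are from Table 1. Diary prompts are from section 6.8.C: three per day, with sleep asked in the morning only. Assumptions: seven days per trial week and every prompt answered.

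Diary, affect: 7 × 3 = 21 in A1, 21 × 3 = 63 in B, 7 × 3 = 21 in A2; total 105. Diary, sleep: 7, 21 and 7; total 35.

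| Measure | Rank in 6.7 | In the 7.3.A list | A1/B/A2 | Total |
|---|---|---|---|---|
| Empatica E4 | primary | yes | 1/3/1 | 5 |
| GAS | primary | yes | 1/3/1 (Table 1) | 5 |
| Lab-TAB | secondary | yes | 1/3/1 | 5 |
| PES-H, PES-C | other | yes | 1/0/1 | 2 |
| PSI-4-SF | other | yes | 1/0/1 | 2 |
| M-ABC-2 | primary | **no** | 1/0/1 | 2 |
| COMPS-2 | primary | **no** | 1/0/1 | 2 |
| SCAS-P | secondary | **no** | 1/0/1 | 2 |
| Daily affect | secondary | **no** | up to 21/63/21 | 105 |
| Daily sleep | secondary | **no** | up to 7/21/7 | 35 |

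The GAS row depends on the source. Section 6.8.C and Table 1 have ratings in weeks 1 through 5, and section 2.2.B agrees (before, during and after the intervention). Section 6.7.A has weeks 1 and 5 only. Under 6.7.A, GAS becomes 1/0/1 and joins the two-point measures.

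**What a 1/0/1 series allows within one child.**

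- *Slope change.* A slope within a phase needs at least two points in that phase. There is one in A1, none in B and one in A2, so no slope exists.
- *SD bands.* For two values differing by d, the SD is d/√2 and each value lies d/2 from the mean. The ratio is (d/2)/(d/√2) = 1/√2 = 0.71, whatever d is. The bands carry no information.
- *Tau-U, A versus B.* It counts A–B pairs. With no B observation there are 2 × 0 = 0 pairs.
- *Hedges g within a child.* A1 against A2 has 1 + 1 − 2 = 0 degrees of freedom, so there is no pooled SD.
- *Exact rank test, A1 against A2.* The smallest two-sided p is 2/C(2,1) = 1.0.

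**Across children**, a paired week 1 to week 5 change with n = 10 has 10 − 1 = 9 degrees of freedom, so a pre-post g can be computed at that level.

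**The case against.** Four points can be made for the plan.

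*The closed list governs the graphs only.* This stands in part. The effect-size sentence names no measures and could cover every outcome, and Table 2 gives M-ABC-2, COMPS-2 and SCAS-P an outcome role. A reader might infer that these measures have no analysis at all; the documents do not support that. They do support the narrower statement that section 7.3 ties no outcome analysis to them explicitly. Likewise, using M-ABC-2 for description does not cancel its outcome role.

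*Method by measure is commonly left to a statistical analysis plan.* True of detail. Here, though, the protocol fixes a list that conflicts with its own outcomes and schedule, and a later plan would have to override it.

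*Hedges g may be meant across children.* Section 7.3.A does not state the level, and section 6.9 seeks preliminary effect sizes from 10 children. The zero-degrees-of-freedom result therefore applies only within a child. The results on slope, SD bands and Tau-U are unaffected.

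*Section 6.8.C is loosely punctuated* and could be read as giving SCAS-P and PES in weeks 1 through 5, which may explain why PES is listed. Sections 6.7.B and 6.7.C and Table 1 settle weeks 1 and 5. Even on the loose reading, PSI-4-SF stays at two points and SCAS-P would then be wrongly omitted.

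Two further inferences go too far. One is that E4, Lab-TAB and GAS should only be plotted. On the Table 1 schedule they have points in every phase, so a phase contrast can be formed. Exact rank p-values within a child cannot fall below 2/C(4,3) = 0.50 (A1 against B) or 2/C(5,3) = 0.20 (both A phases against B), but that limits significance claims, not effect sizes. The other is a false-positive rate for a rank test on serially correlated diary data. The protocol specifies no such test and gives no correlation, so no figure can be attached.

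**Conclusion.** The point holds as an internal contradiction with a practical consequence. Two instruments of a primary outcome and three secondary outcomes (anxiety, affect, sleep) are outside a closed list. Three listed scores (PES-H, PES-C, PSI-4-SF) have a 1/0/1 pattern on which the within-child methods fail. The only data with many points in every phase are omitted. The finding does not show that the trial lacks the data, or that no effect size is possible for the two-point measures.

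The diary counts are maxima that assume seven-day weeks and full response; the finding does not depend on their exact size. The status of GAS, five observations or two, stays open until the protocol is reconciled.

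**What to change.** Rewrite the list in section 7.3.A by schedule.

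- **(a) Time-series display and non-overlap analysis:** E4, Lab-TAB and GAS as now, plus experience-sampled affect and sleep. Reconcile the GAS timing between section 6.7.A and section 6.8.C with Table 1. If weeks 1 and 5 are what is meant, GAS moves to group (b).
- **(b) Measures taken only in weeks 1 and 5 (M-ABC-2, COMPS-2, SCAS-P, PES, PSI-4-SF):** report each child's pre-post change, and the across-child paired change with a 95% CI. State that both visits fall in A phases and that under section 6.8.B the singlet is not in use in week 5. The result is therefore an estimate of carry-over change, not of an effect during wear.

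Keep baseline M-ABC-2 for describing the sample as well, and say in 7.3.B that it serves both purposes. State for each effect size whether it is computed within or across children.

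The cost is analysis wording only. Every measure is already scheduled for collection, and no visit or instrument is added.
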